### 7.1.4 RELAPSE ASSESSMENT

Relapses are defined as the occurrence of new or worsening neurological symptoms attributable to MS, and immediately preceded by a stable or improving neurological state of at least 30 days. Symptoms that persists for more than 24 hrs in the absence of fever and be accompanied by objective neurological worsening consistent with an increase  $\geq 0.5$  on the EDSS (subjects with baseline EDSS of  $>1.0$ ) or an increase  $\geq 1.0$  on the EDSS (subjects with baseline EDSS=0).

Subjects will be assessed for relapse by the treating investigator at each study visit as outlined in the study evaluations table and, if necessary, at unscheduled visits. If a protocol defined relapse does occur, it will be documented in the eDC.

### **MS Relapses during the study:**

Any patient experiencing a multiple sclerosis relapse while on study will be allowed rescue therapy with intravenous methylprednisolone 1gm/day for up to 5 consecutive days. Subjects requiring rescue therapy will have an MRI scan 10 days after completion of treatment with steroids.

### **Re-consent criteria**

In case of a confirmed diagnosis of MS relapse (as defined in the protocol, Appendix C), **or** in case of an increase in EDSS of 1.0 points or more, sustained for at least 3 months, during the study, the following actions will be taken:

3. The subject will be reminded of the current approved MS medications/treatments and the opportunity to terminate the study and be treated with an approved MS medication.
4. The subject will be requested to re-sign an informed consent form if he/she chooses to continue to participate in the study, in the same treatment assignment.

## 7.2 DEFINITIONS

---

**Evaluable for toxicity.** All subjects will be evaluable for toxicity from the time of their first treatment on Day 1.

**Evaluable for radiological and neurological response.** Only those subjects who have had a pre-treatment baseline efficacy evaluation and at least one post-treatment efficacy evaluation will be considered evaluable for response. These subjects will have their response classified according to the definitions stated below.

## 7.3 DISEASE PARAMETERS

---

**Measurable disease:** Diagnosis of RMS will be based on the 2010 McDonald's criteria (Appendix C).

## 7.4 DURATION OF RESPONSE

---

### **Duration of stable disease:**

Stable disease is measured from the start of the treatment until the criteria for relapse or progression of disease are met or there is evidence of new radiological activity as assessed by MRI, taking as reference the smallest measurements recorded since the treatment started, including the baseline measurements.

## 7.5 RESPONSE REVIEW

---

Subjects will be assessed for relapse by the treating investigator at each study visit as outlined in the study evaluations table and, if necessary, at unscheduled visits.

Relapses are defined as the occurrence of new or worsening neurological symptoms attributable to MS, and immediately preceded by a stable or improving neurological state of at least 30 days. Symptoms that persists for more than 24 hrs in the absence of fever and be accompanied by objective neurological worsening consistent with an increase  $\geq 0.5$  on the EDSS (subjects with baseline EDSS of  $>1.0$ ) or an increase  $\geq 1.0$  on the EDSS (subjects with baseline EDSS=0).

## 8 PHARMACEUTICAL INFORMATION

---

### 8.1 UBLITUXIMAB

---

Chemical Name:	Ublituximab
Other Names:	TG-1101
Classification:	Recombinant chimeric anti-CD20 monoclonal antibody
Formulation:	See Investigator Brochure
Mode of Action:	Targets CD20 antigen on B-cells
Description:	Ublituximab is a genetically engineered chimeric murine/human mAb directed against the CD20 antigen found on the surface of B lymphocytes. Ublituximab displays the typical structure of immunoglobulins, consisting of two gamma ( $\gamma$ ) heavy chains and two kappa ( $\kappa$ ) light chains linked by disulfide bridges. It is composed of a murine variable region (37.2% of total amino acids) fused onto human constant regions.
How Supplied:	Concentration of 10 mg/mL in 15 mL (150 mg) single-use glass vials.

**OR**

	Concentration of 25 mg/mL in 6 mL (150 mg) single-use glass vials.
Storage:	Ublituximab must be stored in a secured limited-access area at a temperature ranging +2°C / + 8°C. Ublituximab must not be frozen.
Stability:	Once a vial of ublituximab has been opened and/or diluted it must be used immediately. After dilution, ublituximab is stable in static conditions for 24 hours at 25°C, and in dynamic conditions it is stable for 8 hours at 25°C.  Ublituximab has a shelf-life of 24 months if stored between +2°C / + 8°C, based on stability data

*Route of Administration:* Intravenous

*Packaging:* Ublituximab is packed in unit boxes. Each of the unit boxes contains:

- One 15 mL vial containing 10 mg/mL solution of ublituximab; or
- Unit kit of 6 vials per kit with each vial 15 mL

**OR**

- Six 6 mL vial containing 25 mg/mL solution of ublituximab; or
- One 6 mL vial containing 25 mg/mL solution of ublituximab

The container closure system for the vials containing 6 mL is a type I glass vial closed by a siliconized chlorobutyl rubber stopper sealed with an aqua plastic aluminum cap.

The container closure system for the vials containing 15 mL is a Type I plus borosilicate vial closed by a siliconized bromobutyl rubber stopper sealed with a white plastic and aluminum cap.

*Availability:* Ublituximab is available from TG Therapeutics.

---

### 8.1.1 COMPREHENSIVE ADVERSE EVENTS AND POTENTIAL RISKS LISTS (CAEPRS)

---

The following adverse events were observed in subjects treated with single agent ublituximab and were considered at least possibly related to study medication. See the ublituximab investigator brochure for a complete list of all adverse events reported regardless of causality.

#### 8.1.1.1 COMMON (>20%)

---

- **Blood and lymphatic system disorders:** Neutropenia, Thrombocytopenia
- **General disorders and administration site conditions:** Infusion-related reaction, Pyrexia, Chills
- **Nervous system disorders:** Headache

#### 8.1.1.2 LESS COMMON (10-20%)

---

- **Blood and lymphatic system disorders:** Anaemia
- **Gastrointestinal disorders:** Diarrhoea, Nausea, Abdominal Pain Upper
- **General disorders and administration site conditions:** Fatigue, Asthenia

#### 8.1.1.3 UNCOMMON (ADVERSE EVENTS REPORTED IN AT LEAST 2 PATIENTS BUT < 10%)

---

- **Blood and lymphatic system disorders:** Febrile neutropenia, Pancytopenia
- **General disorders and administration site conditions:** Pain
- **Infections and infestation:** Bronchitis
- **Investigations:** Blood bilirubin increase, Alanine aminotransferase increased, Aspartate aminotransferase increased, Gamma-glutamyltransferase increased, Elevated liver enzymes
- **Musculoskeletal and connective tissue disorders:** Muscle weakness
- **Nervous system disorders:** Dysgeusia
- **Respiratory, thoracic and mediastinal disorders:** Throat irritation/tightness, Dyspnea
- **Skin and subcutaneous tissue disorders:** Pruritus
- **Vascular disorders:** Hypertension

---

### 8.1.2 DISPENSING

---

Before dispensing, the site pharmacist or his/her representative must check that ublituximab is in accordance with the product specifications and the validity is within the re-test and expiry date.

The exact dose and the date and time of administration of ublituximab must be recorded within the CRF, patient's medical records, and/or in the drug accountability records.

The Pharmacist or his/her representative should record the date dispensed and patient's number and initials on the labels. He/she should complete the accountability forms with information concerning the dispensation of ublituximab. Preparation should be done by the Pharmacist or his/her representative according to instructions for sterile dilution included within the unit boxes of ublituximab. Dilution for ublituximab is as follows:

#### 8.1.2.1 DILUTIONS OF UBLITUXIMAB

---

Ublituximab must not be mixed with other medicinal products. Ublituximab should only be diluted in 0.9% NaCl before use. No data are available for other solutions such as 5% dextrose and 5% mannitol.

Ublituximab or IV placebo must not be mixed with other medicinal products.

[REDACTED]

Dose of ublituximab for infusion	[REDACTED]
150 mg	[REDACTED]
450 mg	[REDACTED]
600 mg	[REDACTED]

[REDACTED]

Dose of ublituximab for infusion	[REDACTED]
150 mg	[REDACTED]
450 mg	[REDACTED]
600 mg	[REDACTED]

### 8.1.3 ADMINISTRATION

- IV administration only. Ublituximab should not be administered as an IV push or bolus.
- Ublituximab must be checked before being administered for cloudiness, color, soapy aspect, or deposits.
- Ublituximab must not be administered if does not conform to the specifications. The Investigator or his/her representative must immediately inform the Monitor/Sponsor.
- In accordance with Section 5.3, a list of pre-medication will be administered before infusion of ublituximab.
- Since infusion-related hypotension may occur, **antihypertensive medications should be withheld 24 hours** prior to and throughout infusion of ublituximab
- No other treatment may be co-administered with ublituximab (other than for immediate intervention for adverse event).
- It is recommended that ublituximab be administered immediately after dilution.

Ublituximab should be administered only by slow infusion via intravenous route as a single administration as described below:

- 1st infusion → in approximately 4 hours
- 2nd and 3rd infusion → in approximately 1 to 3 hours, depending on the cohort

The flow rate is specified in the tables below.

#### 8.1.3.1 FLOW RATE RECOMMENDATIONS FOR UBLITUXIMAB ADMINISTRATION

##### **1st infusion over 4 hours for all cohorts**

1ST INFUSION OF UBLITUXIMAB OR PLACEBO

Cohorts	Ublituximab Dose	Total volume to be infused	Infusion rate			
			T0 to T30'	T30' to T1H	T1H to T2H	T2H to T4H
1-3	150 mg	250 mL	10 mL/H	20 mL/H	35 mL/H	100 mL/H

Cohorts	Ublituximab Dose	Total volume to be infused	Infusion rate			
			T0 to T30'	T30' to T1H	T1H to T2H	T2H to T3H
4	150 mg	250 mL	10 mL/H	20 mL/H	85 mL/H	150 mL/H

Cohorts	Ublituximab Dose	Total volume to be infused	Infusion rate		
			T0 to T30'	T30' to T1H	T1H to T2H
5	150 mg	250 mL	10 mL/H	40 mL/H	225 mL/H

Cohorts	Ublituximab Dose	Total volume to be infused	Infusion rate	
			T0 to T30'	T30' to T1H
6	150 mg	250 mL	50 mL/H	450 mL/H

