### 2.1 PRIMARY OBJECTIVES

---

- To determine the level of B cell depletion by ublituximab in subjects with RMS
- To determine the optimal dose and infusion time for ublituximab in subjects with RMS

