## **5.2 AGENT ADMINISTRATION**

---

Treatment will be administered in the MS center. The MS centers must have skilled personnel and adequate equipment to provide emergency treatment should the subject experience anaphylaxis, hypotension or respiratory distress. Subjects will be enrolled into a specified cohort. A single dose of 150 mg of ublituximab on Day 1 with an infusion rate of 4 hours, 450 or 600 mg on Day 15 at different infusion rates (see dosing scheme), and at week 24, a single dose of 450 or 600 mg of ublituximab with different infusion rates will be administered to the respective cohorts. Additionally, 2 subjects in each cohort will be randomized to a placebo group. On day 28, the placebo subjects will begin active treatment with ublituximab in its respective cohort (see dosing scheme). Administration of ublituximab and placebo will be under the direction of the study investigators. Additional dosing cohorts may be explored.

It is required the absolute neutrophil counts and the platelet count should be within normal range before the infusion of ublituximab.

If the liver enzymes (ALT and/or AST) are > 5 times the upper limit of normal (ULN) of the normal range, or if the neutrophil count and platelets counts are below acceptable levels as described, the dose of ublituximab will be held for up to 48 hours until the laboratory values return to within acceptable range. If all labs above do not return to within the acceptable range within 48 hours, the subject will not receive the ublituximab infusion and will be withdrawn from the study. Subjects who are withdrawn will be asked to enter the follow-up evaluation period of the study.

---

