## 9.8 EFFICACY ANALYSES

---

The study is not designed (powered) to detect treatment differences. All efficacy variables will be summarized at all-time scheduled points where they are assessed. If appropriate, dose response or treatment differences may be analyzed. If p-values are presented, they will be nominal p-values without adjustment for multiple tests.

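### The protocol's general administration text gives a 4-hour first infusion, while its dosing tables and flow-rate rows give 3, 2 and 1 hour for Cohorts 4, 5 and 6

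*Protocol*

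**What the plan says.** Three places in the current protocol (Version 8.0) give 4 hours for the first infusion:

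- Section 8.1.3.1, heading of the first-infusion tables: "1st infusion over 4 hours for all cohorts".
- Section 8.1.3, first-infusion bullet: "infusion → in approximately 4 hours". It names no cohort. The next bullet, on the second and third infusions, does vary: "in approximately 1 to 3 hours, depending on the cohort".
- Section 5.2: "A single dose of 150 mg of ublituximab on Day 1 with an infusion rate of 4 hours". The same sentence goes on to say that the Day 15 and week 24 rates differ.

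Two sets of tables give cohort-specific times of 4 h for Cohorts 1 to 3, 3 h for Cohort 4, 2 h for Cohort 5 and 1 h for Cohort 6:

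- The dosing schema (Tables 1, 3 and 6) and the matching schema for placebo subjects after crossover (Tables 2, 4 and 7).
- The step-rate rows in Section 8.1.3.1, directly under the 4-hour heading.

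Section 2.1 lists as a primary objective: "To determine the optimal dose and infusion time for ublituximab in subjects with RMS".

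**The concern.** These are instructions for giving the drug, not background text, and they disagree on the one feature that separates three cohorts. Cohorts 4, 5 and 6 share the same doses (150, 600 and 600 mg) and the same 1-hour infusions on Day 15 and at week 24. Only the first-infusion time differs. If some subjects in these cohorts were infused over 4 hours, the comparison of infusion times would be diluted. With 6 ublituximab subjects per cohort, one such subject is a sixth of the cohort.

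The planned summaries would not readily show it. SAP Section 2.1.2 counts infusions, interruptions, completions and the percentage of the planned infusion received, but does not list actual infusion duration. SAP Section 2.4.5 summarises safety by cohort. An uninterrupted 4-hour infusion in Cohort 6 would therefore be tabulated as a completed Cohort 6 infusion.

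The ambiguity also carries over to a Day 1 dose finished on Day 2, because Sections 6.2.1.2.1 and 8.1.3.3 both refer back to the rate guidance for the first infusion.

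**Working it through.** **Inputs.** Step lengths, rates and the 250 mL total volume come from the first-infusion tables in Section 8.1.3.1. Schema times and cohort sizes come from Tables 6 and 7. The 4-hour figure comes from Sections 5.2, 8.1.3 and the 8.1.3.1 heading.

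**Step 1: volume and time implied by each set of rows.** Volume = sum of (step length in h × rate in mL/h). Time = sum of step lengths.

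| Cohort | Volume from the rows (mL) | Time from the rows | Schema time | General text |
|---|---|---|---|---|
| 1–3 | 0.5×10 + 0.5×20 + 1×35 + 2×100 = 250 | 4 h | 4 h | 4 h |
| 4 | 0.5×10 + 0.5×20 + 1×85 + 1×150 = 250 | 3 h | 3 h | 4 h |
| 5 | 0.5×10 + 0.5×40 + 1×225 = 250 | 2 h | 2 h | 4 h |
| 6 | 0.5×50 + 0.5×450 = 250 | 1 h | 1 h | 4 h |

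The stated 250 mL is reproduced in every cohort. The rows agree with the schema throughout. The general text agrees with both only for Cohorts 1 to 3. Section 8.1.3.1 therefore contradicts itself as well as the schema.

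**Step 2: size of the discrepancy.** Mean rate = 250 mL ÷ time.

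- Over 4 h: 250/4 = 62.5 mL/h.
- Cohort 4: 250/3 = 83.3 mL/h, which is 4/3 = 1.33 times as fast.
- Cohort 5: 250/2 = 125 mL/h, 4/2 = 2 times as fast.
- Cohort 6: 250/1 = 250 mL/h, 4/1 = 4 times as fast.

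These ratios measure the gap between the texts. They do not estimate an effect on subjects or results.

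**Step 3: subjects covered.** Ublituximab: 3 cohorts × 6 = 18. Placebo then crossover: 3 × 2 = 6. Together 24 of 6 × 8 = 48 planned, before any expansion.

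**Step 4: what each general statement covers.** Only the 8.1.3.1 heading names all cohorts. Sections 5.2 and 8.1.3 are unqualified. A reader would take them as general, because each says that the later infusions vary and does not say so of the first.

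**The case against.** The strongest reply is that the instruction a site actually runs is clear. Infusions are set in mL/h, and the step tables are labelled by cohort. Section 8.1.3 sends the reader to those tables, and no 4-hour step table exists for Cohorts 4, 5 or 6. To follow the heading, a site would have to pass over the row for its own cohort and use the one labelled 1–3. Sections 5.2.1.1, 6.2.1.2.1 and 8.1.3.3 treat infusion rates as cohort-specific targets and require a decision to slow or interrupt to be recorded. Section 5.2.1.2 requires the date and time of administration to be recorded.

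This stands as far as likelihood goes: a site using its own row would match the schema. It does not remove the contradiction.

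A reader might infer that all three places explicitly prescribe 4 hours for every cohort. Only the heading does.

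A reader might also infer that the comparison of infusion times has been lost. The documents do not support that. It would require sites to prefer the heading or narrative to their own rate row, and nothing shows that any did. Nor is there a formal test to lose. Section 9.8 says "The study is not designed (powered) to detect treatment differences", and the only trend test mentioned is an optional one for dose response (Protocol Section 9.8.1, SAP Section 2.4.2). What could suffer is a descriptive comparison, though one that serves a primary objective.

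**Conclusion.** The point holds as an internal inconsistency in current administration text. One heading gives 4 hours for all cohorts and two sections give 4 hours without a cohort limit, against 3, 2 and 1 hour in the schema tables and rate rows for Cohorts 4, 5 and 6. It covers 3 of 6 cohorts and 24 of 48 planned subjects, with up to a fourfold difference in stated duration. It is worth correcting because it concerns the only planned difference between those cohorts and because infusion time belongs to a primary objective. The chance of an actual error is reduced by the cohort-labelled rows, and the documents give no way to estimate it.

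The conclusion assumes that the unqualified statements in Sections 5.2 and 8.1.3 are meant generally, which their wording suggests but does not state. The subject counts are the planned ones, before expansion.

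Two further inferences should be resisted. The first is that the design itself is at fault; the schema tables are consistent with one another. The second is that the schema times must be right and the 4-hour text wrong. Cohorts 4 to 6 were added in Versions 5.0 and 6.0, so wording not updated at that point is a possible explanation, but the documents do not say so. Which duration applies is for the sponsor to settle.

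**What to change.** The sponsor should confirm the intended first-infusion duration for each cohort. Section 5.2, the first-infusion bullet in Section 8.1.3 and the heading in Section 8.1.3.1 should then be reconciled with the schema tables (Tables 1 to 4, 6 and 7) and the flow-rate rows, so that every place states the same duration for a given cohort.

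The cost is small: if the tables stand as confirmed, three wording edits. If the confirmation goes the other way for any cohort, the tables and rate rows need changing as well.

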## 2nd infusion

### 2ND INFUSION OF UBLITUXIMAB OR PLACEBO

Cohort	Ublituximab Dose	Total volume to be infused	Infusion rate		
			T0 to T1H	T1H to T2H	T2H to T3H
1	450	250 mL	25 mL/H	75 mL/H	150 mL/H

Cohort	Ublituximab Dose	Total volume to be infused	Infusion rate	
			T0 to T30 min	T30 min to T90min
2	450	250 mL	100 mL/H	200 mL/H

Cohort	Ublituximab Dose	Total volume to be infused	Infusion rate	
			T0 to T30min	T30min to T60min
3	450 mg	250 mL	100 mL/H	400 mL/H

Cohort	Ublituximab Dose	Total volume to be infused	Infusion rate	
			T0 to T30min	T30min to T60min
4-6	600 mg	250 mL	100 mL/H	400 mL/H

## 3rd infusion

### 3RD INFUSION OF UBLITUXIMAB

Cohort	Ublituximab Dose	Total volume to be infused	Infusion rate	
			T0 to T30min	T30min to T90min
1	450	250 mL	100 mL/H	200 mL/H

Cohort	Ublituximab Dose	Total volume to be infused	Infusion rate	
			T0 to T30min	T30min to T60min
2	450	250 mL	100 mL/H	400 mL/H

Cohorts	Ublituximab Dose	Total volume to be infused	Infusion rate	
			T0 to T30min	T30min to T60min
3-6	600mg	250 mL	100 mL/H	400 mL/H

#### 8.1.3.2 AGENT HYPERSENSITIVITY

**Ublituximab Hypersensitivity and Infusion Reactions:** Available at the bedside prior to ublituximab administration will be medications and resuscitation equipment for the emergency management of anaphylactic reactions per institution guidelines. Ublituximab should be administered intravenously through a dedicated line.

#### 8.1.3.3 INFUSION RATE REDUCTIONS DUE TO INFUSION RELATED REACTIONS

The following are recommended infusion rate reduction/delay guidelines for subjects who experience severe Infusion Related Reactions (IRR's) in which treatment must be interrupted. The final decision for the infusion rate

TG1101-RMS201

Dated: 10 October 2017 (Ver. 8.0)

reduction/delay or discontinuation resides with the treating investigator. Infusion rates should be considered targets for each respective cohort. If the treating investigator decides to interrupt the infusion or slow the infusion rate, then the reduction/delay and the reason for it must be noted on the eCRF and infusion log.

**1st Dose Interruption:**

- The patient must be closely monitored until complete disappearance of symptoms.
- Following the judgment of the Investigator, and provided vital signs are stable and normal saline has infused for at least 30 minutes, the infusion may or may not be resumed at maximum 50% of previous rate.
- The rate should be increased by 50% every 30 minutes to the max rate of 100 mL/hr as long as tolerated.

**2nd Dose Interruption (same day):**

- Wait a minimum of 2 hours
- After 2 hours, the patient must again be closely monitored until complete disappearance of symptoms.
- Following the judgment of the Investigator, and provided vital signs are stable and normal saline has infused for at least 30 minutes, the infusion may or may not be resumed at maximum 50% of previous rate.
- The rate should be increased by 50% every 30 minutes to the max rate of 100 mL/hr as long as tolerated.

If there is a second interruption of treatment due to IRR symptoms, ublituximab infusion must be stopped. The treating physician may decide whether to attempt completion of the infusion on a second day. Clinical investigators and clinical monitors familiar with the clinical course of MS must use their judgement and determine the tolerability of a given dose of ublituximab.

- If the dose is discontinued on Day 1, administration of the remainder of the dose on Day 2 is permitted as follows:
  - On Day 2, if patient symptoms have resolved, estimate remaining dose needed and prepare accordingly for infusion.
  - Begin infusion of remaining dose according to the infusion rate guidelines presented above for the first infusion of ublituximab.

If the patient has a dose interruption on Day 2, discontinue the infusion. The patient should again be monitored for all symptom resolution prior to release from trial site. The patient should start their next scheduled weekly infusion at the protocol specific dose (Day 15), at the infusion rate indicated in Section 8.1.3.1 for 2nd and 3rd infusions. If infusion rate reductions should be needed for the week 24 infusion, please refer to the above recommendations. Final decision for infusion rate reduction/delay or discontinuation resides with the treating investigator. Clinical investigators and clinical monitors familiar with the clinical course of MS must use their judgement and determine the tolerability of a given dose of ublituximab.

